## 1 Abstract

Rheumatoid arthritis (RA) is a common autoimmune disease which causes inflammation in the joints and resulting disability. RA has a significant impact on a person's quality of life and carries a heavy financial burden both to the individual and to society. Its' causes remain unknown, however the discovery of alterations in the populations of microbes that normally reside in the gut in RA patients has highlighted the potential of gut microbes being involved in the development of RA. This study will investigate this possibility further by examining the bacteria and viruses resident in the gut of 30 patients with early rheumatoid arthritis. To evaluate the importance of gut bacteria and viruses in the development and successful treatment of RA with methotrexate, stool samples will be collected at 3 time points: a) before treatment, b) during treatment and c) following maintenance or escalation of treatment based on a successful or unsuccessful response, respectively. We will also explore if patients with RA have a leaky gut (increased intestinal permeability) and develop an aberrant immune response to their own gut microbes as a result of them gaining access to the bloodstream, and whether this is altered with methotrexate treatment. Furthermore, as diet and lifestyle affect RA activity and progression and can influence the activity of gut microbes, dietary and lifestyle data will be collected to identify potential covariants with disease onset or progression. The outcomes of this project will help identify microbiome-based predictive factors associated with response to methotrexate, and a clearer understanding of the interplay between gut microbes, intestinal permeability and environmental factors in the development of RA.

**Figure 1. Proposed mechanism of the gut-joint axis in inflammatory arthritis (Jethwa, 2017)**

## 2 Scientific Background

### 2.1 RA epidemiology and clinical treatment

Rheumatoid arthritis (RA) is a chronic autoimmune condition characterized by inflammation of the joints that affects approximately 0.3-1% of the world population. Its causes are unclear. Although linked with genetic predisposition, low concordance of RA among genetically identical twins suggests a significant contribution of environmental factors. RA may be either seropositive or seronegative, based on the respective presence or absence of the autoantibodies anti-cyclic citrullinated peptide (anti-CCP; directed against various joint components) and/or rheumatoid factor (RF; directed against immunoglobulin G).

Oral methotrexate (MTX) is the standard initial treatment provided for early RA. It is one of several disease-modifying anti-rheumatic drugs (DMARDs) which may be used in combination if MTX monotherapy is ineffective. The disease-activity lowering effects of MTX are only seen at a clinically important level (i.e. a reduction of  $\geq 1.2$  in the Disease Activity Score [DAS]) in approximately 34% of patients. MTX; which has various side effects including increased risk of infection, is therefore sometimes used with little or no clinical benefit to the patient. There are no reliable predictors of MTX response, although those concomitantly using steroid injections (prednisolone) and of the male sex are more likely to respond well. As some gut bacteria are able to assimilate and chemically alter MTX *in vitro*, it is possible that the composition of the gut microbiome might be involved in MTX response.

### 2.2 Microbial dysbiosis and “leaky gut” in RA

The vast population of microbes that inhabit the human gut, i.e. the microbiota, includes a wide variety of bacteria, fungi and viruses. The composition of these microbes is altered (microbial dysbiosis) in some chronic conditions including RA. A gut-joint axis (Figure 1) has been proposed for RA pathogenesis whereby microorganisms in the gut are able to influence disease initiation and progression, potentially via increased intestinal permeability (“leaky gut”) and microbial dysbiosis. However, although several studies have identified microbial dysbiosis in RA patients, it is not clear how these changes contribute to disease outcomes.

The microbiota alterations identified so far in RA have generally consisted of a reduced diversity of bacteria, coupled with increased or decreased abundance of individual microbial taxa. For instance, abundance of *Prevotella copri* is associated with new-onset RA, and *Collinsella*; which has the ability to alter intestinal permeability possibly allowing microbial/dietary components in the gut lumen to access host immune structures, is also increased in abundance RA. On the contrary, potentially beneficial bacteria such as *Faecalibacterium* are depleted in some RA patients. The relevance of these alterations to RA treatment is unknown, although some differences in the abundance of specific bacteria between responders and non-responders to MTX and herbal medications have been observed. This suggests the involvement of gut microbes in response to MTX, potentiating the use of gut microbiota profiles as a predictive tool for response, or the use of microbiota-altering strategies to improve treatment outcome.

The gut-joint axis theory encompasses the possibility that the autoimmune response seen in RA may arise as a result of immune responses against antigens in the gut (microbial or dietary), which are cross-reactive with antigens expressed by human cells (molecular mimicry). These immune responses may be enabled by an increase in intestinal permeability. There is variable evidence of increased intestinal permeability in RA patients, which may also be influenced by gut microbes such as *Collinsella*. However, little is known about any specific immune responses against gut microbes, or how immune cells respond to the expanded subsets of microbes in RA. Elucidating if

microbial dysbiosis and/or an immune response against gut microbes effects disease severity and response to treatment is important to make microbiome research translatable and identify targets for the improvement of treatment strategies.

### 2.2.1 The gut virome in RA

Gut viruses (the virome) are a largely overlooked component of the human gut microbiome which is surprising as they represent its largest component. A major factor in our limited understanding of the gut virome is the lack of suitable tools and analytical methods. The virome consists mainly of viruses that infect bacteria (phages), which most likely control the structure and function of bacterial populations in the gut. Like bacterial populations, the composition of viruses in the gut varies according to environmental factors such as diet and antibiotics.

A study of the virome in inflammatory bowel disease (IBD) demonstrated changes to the intestinal virome in a disease state, with an increase in the number of different viruses present and an associated decrease in bacterial populations, suggesting a predator-prey relationship between the two. The intestinal virome has not yet been characterized in patients with RA, though as phages are able to significantly alter bacterial populations it is possible they may be initiating factors for microbial dysbiosis or alter the abundance of MTX response-associated bacteria. Alternatively, the ability of viruses to cross the intestinal barrier, gain entry to the body and induce host immune responses could provide a trigger for the generation of cross-reactive antibodies in RA.

## 2.3 Diet and RA

Environmental factors such as smoking, diet, and infection are associated with risk of RA. Many of these factors also influence the composition of the human gut microbiome. Microbiome studies therefore need to account for environmental factors to provide a more comprehensive and insightful analysis, although this is not always done. For instance, dietary analysis has been absent from microbiome studies in RA, despite diet being a potential causal factor in disease-associated microbial dysbiosis. RA patients often feel that their symptoms are associated with dietary fluctuations, and diet represents an easily modifiable risk factor for RA. However, little reliable evidence exists for the benefits of using dietary intervention to improve RA disease activity, and no studies have been carried out to assess whether diet is associated with RA treatment response or response-associated microbiota profiles. Identifying dietary components associated with microbial dysbiosis in RA could enable the generation of personalized treatment programs incorporating diet recommendations, which would be a simple and cost-effective way of enhancing treatment response in RA.

## 2.1 Summary

Microbial dysbiosis has been established in RA in several studies, although the cause of dysbiosis and its relevance to clinical management of RA is unknown. Additionally, the ability of microbes in the gut to initiate immune responses contributing to RA; possibly via increased intestinal permeability, is not well understood. This study will primarily investigate whether gut microbial dysbiosis; or more specifically microbial diversity (Shannon index), is associated with MTX treatment response in RA. This will build on a previous study in which differences in the abundance of specific bacterial groups were identified between responders and non-responders to MTX, by defining a more specific early RA cohort on MTX monotherapy, characterizing changes to the viral as well as bacterial components of the microbiome, investigating intestinal permeability in these participants and exploring microbiome associations with diet and lifestyle factors. We will investigate longitudinal changes to the microbiota induced by MTX over 6 months and attempt to correlate a continuous microbiome parameter ( $\alpha$ -diversity/Shannon index) with change in DAS28-C-reactive protein (DAS28-CRP).

Correlations between specific microbial abundances; including that of viruses, and treatment response will also be identified. Together, these analyses will help identify response-associated microbiota alterations prior to and during MTX treatment, which could be targeted to improve MTX treatment response. Any response-associated microbiota alterations will be tested for association with diet and lifestyle variables, to provide insight into whether these alterations could be caused by environmental factors affecting the microbiota. Finally, we will investigate whether systemic immune responses against gut microbes are present in RA, which could suggest increased intestinal permeability and a possible “gut origin” for RA.

### 3 Hypothesis

A single microbiome parameter ( $\alpha$ -diversity, microbial diversity measured by Shannon index) in treatment-naïve early RA patients positively correlates with MTX response at 3 months (measured by change in DAS28- CRP) and can be used to predict treatment response in these patients.

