## 7 Statistical methods

### 7.1 Sample size calculations

Sample size calculations were carried out by [name], a QIB statistician. Previous studies suggest that change in DAS28 score in response to treatment has a standard deviation of 1 to 1.3 points. The minimum clinically relevant difference in DAS28 has been reported in two different studies as 1-1.2 points.

Hence, to detect a clinically relevant difference in DAS28 we will aim to recruit enough participants to estimate an effect size of one standard deviation in the outcome per two standard deviations in Shannon index, corresponding to a correlation coefficient of 0.5, typically considered a large effect. This will require 30 subjects to complete the study (true power=82.5%, size=0.05), hence our target sample size for recruitment is 35, allowing for 5 participants to drop-out of the study. Using the change score from baseline to the mean of two follow-up responses as the primary outcome will slightly improve the power of the study but it is difficult to know by how much without prior information on the longitudinal variation of DAS28. Power calculations were conducted using the *pwr* package in R.

Multivariate analyses linking detail of the structure and composition of the microbiome to outcomes are purely exploratory and will be reported as such.

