### 7.2 Statistical methods for the analysis of study data

#### 7.2.1 Correlating microbiome parameters with treatment outcome

Spearman's correlation coefficient will be used to identify statistically significant associations between (continuous variables) Shannon index at baseline and change in DAS28-CRP from baseline to 3 months post-MTX. In addition, Shannon index and other microbiome characteristics such as taxa and gene abundance will be analysed for covariation with other clinical metadata (CRP, anti-CCP, RF), also using Spearman's correlation coefficient. The predictive capability of the microbiome for MTX response will be assessed by generation of a cross-validated predictive model, using a machine-learning R statistical package such as *randomForest*.

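### The hypothesis claims that baseline Shannon index alone can predict methotrexate response, but the plan tests only its association with response

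*Protocol*

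**What the plan says.** Section 3 makes two statements about one variable, baseline Shannon index. It correlates positively with response at 3 months, and it "can be used to predict treatment response in these patients".

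The sections that put this into practice are:

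- **Section 4.1** frames the primary aim as estimating the correlation between Shannon index and change in DAS28-CRP.
- **Section 7.1** sizes the study for an effect "corresponding to a correlation coefficient of 0.5, typically considered a large effect", and continues: "This will require 30 subjects to complete the study (true power=82.5%, size=0.05". It also labels multivariate work linking microbiome structure and composition to outcomes as exploratory.
- **Section 7.2.1** fixes a Spearman correlation of baseline Shannon index with change in DAS28-CRP to 3 months. It then adds: "The predictive capability of the microbiome for MTX response will be assessed by generation of a cross-validated predictive model". A package such as randomForest is given as the tool.
- **Section 5.9.2.2** plans a comparison of diversity (Shannon index is one example) and of genera between responders and non-responders, and says this will bear on how reliable microbiome parameters are as predictors.

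**The concern.** Correlation and prediction are different claims. A test of zero correlation can reject when the variable says little about an individual patient's outcome. The second half of the hypothesis concerns Shannon index by itself, yet the one analysis fixed specifically for that variable and the 3-month outcome tests association.

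The machine-learning model does not fill the gap. If a model with many features does well, that does not show that Shannon index predicts. If it does badly, that does not show that Shannon index fails. A difference in diversity between responders and non-responders is a further form of association.

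Followed as written, the plan leaves the predictive half of its only stated hypothesis either unanswered or resting on association. Section 2.1 says that no reliable predictor of methotrexate response exists, so a claim to have found one would carry weight.

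**Working it through.** **Inputs, all from section 7.1.** There are n = 30 completers, alpha is 0.05 and the design correlation is r = 0.5. The change in DAS28 "has a standard deviation of 1 to 1.3 points". The minimum clinically relevant difference "has been reported in two different studies as 1-1.2 points". Sidedness is not stated.

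**Step 1: reproduce the stated power.** The method is power for a Pearson correlation by Fisher's z with the small-sample bias term, two-sided.
- Critical t on 28 df = 2.048, so critical r = sqrt(t² / (t² + 28)) = 0.361.
- z under the alternative = atanh(0.5) + 0.5 / (2 × 29) = 0.558.
- z at the critical value = atanh(0.361) = 0.378.
- Power = Φ((0.558 − 0.378) × sqrt(27)) = 82.5%, as stated. A one-sided test would give 89.5%, so the calculation was two-sided.
- Recruitment: 30 / (1 − 5/35) = 35, as stated.

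**Step 2: variance explained.**
- Just significant: 0.361² = 13%. The residual SD falls by 1 − sqrt(1 − 0.130) = 7%.
- Design value: 0.5² = 25%. The residual SD falls by 1 − sqrt(0.75) = 13%.
- The 95% confidence interval for the correlation (Fisher z, n = 30) is about 0.00 to 0.64 in the first case and 0.17 to 0.73 in the second.

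**Step 3: prediction error for one patient.**
- Residual SD = SD × sqrt(1 − r²).
- 95% prediction half-width at the mean of Shannon index = 2.048 × SD × sqrt((1 − r²) × 29/28) × sqrt(1 + 1/30).
- For example, with r = 0.5 and SD 1: 2.048 × 0.881 × 1.017 = 1.84.
- The last two rows assume normal errors: 2 × (1 − Φ(limit / residual SD)).

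| Quantity | r = 0.361, SD 1 to 1.3 | r = 0.5, SD 1 to 1.3 |
|---|---|---|
| Residual SD (points) | 0.93 to 1.21 | 0.87 to 1.13 |
| 95% prediction half-width (points) | 1.98 to 2.57 | 1.84 to 2.39 |
| Patients with error above 1 point | 28% to 41% | 25% to 37% |
| Patients with error above 1.2 points | 20% to 32% | 17% to 29% |

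Every half-width exceeds 1.2 points. The residual SD does not: with SD 1 it is below 1 point at both correlations.

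**The case against.** The strongest reply is that prediction is planned for. Section 7.2.1 has a cross-validated model in which Shannon index could be one feature, and section 5.9.2.2 names Shannon index in a comparison said to inform on predictors. A reader might infer from section 3 that the protocol has no prediction analysis at all. These two sections show otherwise. What remains is narrower: neither isolates Shannon index, and only the first involves cross-validation.

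A second reply is that feature lists and performance measures belong in a statistical analysis plan, which is not shown. That is fair, and their absence is not the point here. The point is that section 3 claims more than sections 4.1, 7.1 and 7.2.1 set out to show.

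A third is that the harm is hypothetical. The operative sections speak of association, and section 7.1 promises that the multivariate work will be reported as exploratory. A reader might infer that the protocol lets the correlation p-value stand as proof of prediction. No passage says so. But section 3 joins the two claims, and section 5.9.2.2 treats a group difference as evidence about predictors, so the wording leaves that reading open.

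A fourth is that the protocol sets no standard of accuracy for individuals, and that a 95% half-width is a demanding one. By the formula above, a half-width of 1.2 points needs r of about 0.82 (SD 1) or 0.90 (SD 1.3). This stands as a caution. The figures show what a significant correlation can leave open, not that Shannon index fails a protocol criterion. Nor do they show that typical error always exceeds the clinically relevant difference.

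**Conclusion.** The mismatch is real but modest. The primary correlation test is unaffected; what is affected is the claim that may be drawn from it. A result that confirms the first half of the hypothesis may explain as little as 13% of variance, with 95% prediction half-widths of about 2.0 to 2.6 points. Even at the design value they are about 1.8 to 2.4 points, against a clinically relevant difference of 1 to 1.2.

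These figures assume a two-sided test, a linear relation with roughly normal errors, and the protocol's SD range. They treat r as a Pearson correlation, as the sample size calculation does; the planned Spearman coefficient has no direct reading as variance explained. Measures of responder classification would need further assumptions, including a responder share that section 2.1 takes from an outside study, so the conclusion does not rely on them.

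**What to change.** In section 3, limit the confirmatory hypothesis to the correlation between baseline Shannon index and 3-month change in DAS28-CRP. That alone removes the mismatch, and the machine-learning model can stay as exploratory work.

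If the predictive clause is kept:

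- Label it exploratory.
- Add to section 7.2.1 a leave-one-out cross-validated R² and prediction error for change in DAS28-CRP from Shannon index alone, with a 95% confidence interval.
- State that any claim of prediction rests on that result, and not on the correlation p-value or the responder comparison in section 5.9.2.2.

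A model with baseline DAS28-CRP as comparator is optional. It answers a different question, namely what Shannon index adds.

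The cost is a sentence in section 3 and, if the second route is taken, a few lines of analysis on data already being collected. No extra patients or visits are needed. The drawbacks are a narrower headline claim and a cross-validated estimate that will be imprecise with 30 patients.

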### 4 Study objectives

This study has been designed primarily to provide information about changes in gut bacteria and viruses of RA patients undergoing treatment with MTX. The primary outcome in this study is DAS28-CRP (a measure of disease activity recorded at every routine clinical appointment) studied as a continuous variable. More information on the collection of disease activity variables including DAS28-CRP can be found in Section 5.7.

#### 4.1 Primary aim

To determine alterations in gut bacteria and viruses of early RA patients and if specific changes are associated with the outcome of MTX treatment, by estimating the correlation between microbial diversity ( $\alpha$ -diversity measured by Shannon index) and response to MTX measured by change in DAS28-CRP.

#### 4.2 Secondary aims

1. To explore more broadly the correlations between baseline gut microbiome parameters; such as compositional and functional profiles, and MTX outcome or disease severity measured by DAS28-CRP, Simplified Disease Activity Index (SDAI), CRP, ESR or autoantibody titer.
2. To explore longitudinal alterations to the composition of gut bacteria and viruses in early RA patients throughout 6 months of MTX treatment.
3. To explore if environmental factors such as diet and lifestyle can be used to explain response-associated alterations in bacterial and/or viral populations in early RA patients.
4. To determine if RA patients generate autoimmune responses to their own intestinal microbes (indicative of increased intestinal permeability) and if this changes with treatment, by testing the humoral (antibody) and cellular (peripheral blood mononuclear cell [PBMC]) reactivity against commensal microbes.

### 5 Study design and methods

#### 5.1 Timeline

[figure not shown]
A prospective cohort of 30 early RA patients will be recruited to complete this study, with data collection taking place at 3 time points: a) before treatment, b) during treatment (3 months) and c) following treatment maintenance or escalation depending on successful or unsuccessful response (6

months). An outline of the study is provided in Figure 2, study flowchart describing the involvement of participants in the study in Figure 3, and data collection time points in Figure 4.

## 5.2 Setting

Sample processing and data analysis will take place using facilities available at the Norwich Research Park (NRP) in Norwich, including the Quadram Institute Bioscience (QIB) and University of East Anglia (UEA) including the Bob Champion Research and Education Building (BCREB). Identification of participants will take place mainly at the Norfolk Arthritis Register (NOAR) office at UEA, and recruitment of further participants may take place at the Rheumatology Department at Norfolk and Norwich University Hospital (NNUH) or at participating General Practitioner (GP) clinics around Norfolk. Study visits will coincide with routine appointments and take place at the Rheumatology Department at NNUH.

**Figure 2.** Study outline

